### **Awake Trigger Compliance**

Awake trigger compliance is determined from the 'Study Product Use' eDiary pages and calculated as:

- Awake trigger compliance (%) = (Number of days the answer to "Did you click the event trigger at awake yesterday?" is "Yes" ÷ Total Number of Days in Treatment Phase) \* 100.

### **Bedtime Trigger Compliance**

Bedtime trigger compliance is determined from the 'Study Product Use' eDiary pages and calculated as:

- Bedtime trigger compliance (%) = (Number of days the answer to "Did you click the event trigger at bedtime yesterday?" is "Yes" ÷ Total Number of Days in Treatment Phase) \* 100.

## **7.4.7 Efficacy Variables**

### **7.4.7.1 Primary Efficacy Variable**

For primary analysis, average minutes of MVPA on Day 7 will be calculated over all non-missing days between study day 1 (product usage) through 7, inclusive and it is collected via the Actigraph device. Average minutes of MVPA on Day 14 will be calculated over all non-missing days between study day 8 through 14, inclusive. Average minutes of MVPA on Day 21 will be calculated over all non-missing days between study day 15 through 20, inclusive. Any days beyond day 20 will be excluded from all summaries and analyses and will only be present in listed data.

Average baseline MVPA is computed as:

- Average baseline MVPA = total minutes of MVPA over the baseline period / number of days with non-missing data over the baseline period.
  - Baseline period is defined in section 7.1.

Average MVPA for each 7-day period is calculated as:

- Average MVPA for 7-day period = total minutes of MVPA over the period / number of days with non missing data over the period.
  - If every day within the 7 – day period has non missing data, then the Average MVPA for 7- day period will be computed as: total minutes of MVPA over the period / 7.

Change from baseline is calculated as:

- Average MVPA for 7-day period - Average baseline MVPA.

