## 1. Document History

Document Version	Date	Reason for changes
1.0	29OCT2024	Final version
2.0	05DEC2024	
Updates from the DRM:
 

• Section 7.1: Date of Last Study Treatment Administration updated include data collected in the End of Study Termination CRF

• Section 7.1: Study day definition updated to:

◦ Study Day = Date of assessment/event – Date of Baseline Visit.

• Section 7.1 Baseline derivation updated in line with new study day definition.

• Section 7.4.7 updated to exclude day 21 in the analysis due to Day 21 being a partial day.

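### The SAP divides a complete period's MVPA by 7, but Week 3 now has six analysed days, so this rule would understate complete wearers' Week 3 MVPA by 14%

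*SAP*

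**What the plan says.** SAP Section 7.4.7.1 defines three post-baseline averages of MVPA. Week 1 is "calculated over all non-missing days between study day 1 (product usage) through 7, inclusive". Week 2 uses days 8 to 14. For Week 3: "Average minutes of MVPA on Day 21 will be calculated over all non-missing days between study day 15 through 20, inclusive". The section adds: "Any days beyond day 20 will be excluded from all summaries and analyses". The document history explains the shorter third window: "Section 7.4.7 updated to exclude day 21 in the analysis due to Day 21 being a partial day".

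The same section then gives the formula for each period: "total minutes of MVPA over the period / number of days with non missing data over the period". A sub-bullet under it covers complete data: "If every day within the 7 – day period has non missing data", the average "will be computed as: total minutes of MVPA over the period / 7".

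The baseline average is total minutes divided by the number of non-missing baseline days. Protocol Section 13.3.1 still defines Week 3 as days 15 to 21.

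**The concern.** For a subject with all Week 3 days observed, one section gives two divisors. The general formula gives 6 and the sub-bullet gives 7. Following the sub-bullet spreads six days of activity over seven.

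The sub-bullet cannot easily be confined to Weeks 1 and 2. The SAP uses the seven-day label for every post-baseline period, both in Section 7.4.7.1 and in the wear-time rule of Section 8.2. The only change-from-baseline formula for MVPA is also written for a seven-day period. If Week 3 were not such a period, the SAP would have no formula for its change score.

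This is the primary endpoint. Week 3 values feed both the global test and the Week 3 estimate in SAP Section 8.2.2. The error would fall only on subjects with complete Week 3 data, so it would make the endpoint depend on how fully the device was worn.

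**Working it through.** **Inputs from the documents**

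- Windows: days 1–7, 8–14 and 15–20 (SAP 7.4.7.1).
- Divisor for a complete period: 7 (sub-bullet, SAP 7.4.7.1).
- Divisor otherwise: number of non-missing days (general formula, SAP 7.4.7.1).
- Baseline divisor: number of non-missing baseline days (SAP 7.4.7.1).
- Minimum for inclusion: 3 valid days in each period (SAP 8.2).
- Planned standardised effect: 0.25 (SAP 3.2.1).

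**Step 1. Does the divisor of 7 match each window?** Days in window = last − first + 1.

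| Period | Days | Count | Ratio to 7 |
|---|---|---|---|
| Week 1 | 1–7 | 7 | 1.000 |
| Week 2 | 8–14 | 7 | 1.000 |
| Week 3 | 15–20 | 6 | 0.857 |
| Week 3, protocol | 15–21 | 7 | 1.000 |

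The divisor fits Weeks 1 and 2 and the protocol's Week 3. It does not fit the SAP's Week 3.

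**Step 2. Relative error.** For a true Week 3 level of M min/day, the six-day total is 6M. The sub-bullet gives 6M/7 = 0.857M, so the relative error is 6/7 − 1 = −14.3%.

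**Step 3. Error in the change score.** Baseline is divided correctly, so nothing cancels. The shift is 6M/7 − M = −M/7. The documents give no MVPA level, so M is assumed:

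| Assumed M (min/day) | 10 | 20 | 30 | 45 | 60 |
|---|---|---|---|---|---|
| Shift (min/day) | −1.4 | −2.9 | −4.3 | −6.4 | −8.6 |

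Two illustrations with assumed values, each with a true change of +5:

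- Baseline 30, Week 3 35: 35 × 6/7 = 30.0, so the change is recorded as 0.
- Baseline 60, Week 3 65: 65 × 6/7 = 55.7, so the change is recorded as −4.3.

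**Step 4. Who is affected.** A subject with 3, 4 or 5 non-missing days in Week 3 is divided by 3, 4 or 5 and has no error. Only a subject with all six days is divided by 7. If a share p of analysed subjects is complete in Week 3 and their mean level is M, the group mean shifts by −pM/7.

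**Step 5. Size against the planned effect.** In units of the standard deviation (SD) of change, the shift for an affected subject is −(M/SD)/7. The documents do not give M/SD. For assumed ratios of 0.5, 1, 1.5 and 2 the shift is −0.07, −0.14, −0.21 and −0.29, against the planned effect of 0.25.

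**The case against.** The strongest reply is that the text does not force the error. The only sentence specific to Week 3 averages over the non-missing days from 15 to 20, and the general formula agrees; both give 6 for a complete wearer. The sub-bullet can be read as the full-week case of that formula. As Day 21 is excluded, Week 3 can never have seven contributing days, so on that reading the condition is never met. SAP Section 5.3 also requires double programming, a sensibility review and an independent senior review, any of which might expose the discrepancy. Finally, SAP version 1.0 is not available, so it is an inference that the divide-by-7 line predates the exclusion of Day 21.

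Much of this stands. The understatement arises only if the sub-bullet is programmed for Week 3, and the history is unconfirmed. But the benign reading has to set aside the SAP's own use of the seven-day label for all three periods. Quality control against the SAP cannot settle the matter when the SAP holds both rules: two programmers who both follow the sub-bullet will agree on the wrong value. In Weeks 1 and 2 the sub-bullet adds nothing, because seven non-missing days already give a divisor of 7. Week 3 is the only place where it can change a result, and there it is wrong.

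**Conclusion.** The concern holds. The primary endpoint derivation contradicts itself for Week 3, and the explicit complete-data rule is wrong for a six-day window. Applied as written, it understates complete wearers' Week 3 MVPA by 14.3% and carries M/7 minutes per day in full into the change from baseline. The percentage follows from the SAP's own day counts. The figures in minutes and in SD units rest on assumed activity levels. The effect on the group mean also depends on the share of complete wearers, which the documents do not give. The bias is conditional on which rule is programmed; the contradiction is not. Weeks 1 and 2 are unaffected, and the sample size does not depend on this point.

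**What to change.** Delete the divide-by-7 sub-bullet from SAP Section 7.4.7.1, so that the general formula governs every period. State that the divisor is the number of non-missing analysed days, at most 7 in Week 1, 7 in Week 2 and 6 in Week 3, and label the third period as Days 15–20. Check that any existing program for the MVPA dataset uses the same divisor.

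The cost is one deleted line and a short clarification in the SAP, with no new data and no change to the model. The steps, cadence, gait speed and morning stiffness derivations have no divide-by-7 line, so correcting the seven-day label there is editorial only.

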### **7.4.7.2 Secondary Efficacy Variables**

#### **Change from baseline on Days 7, 14, and 21 in Daily Average number of steps taken**

Average baseline number of steps taken is calculated as:

- Average baseline number of steps taken = total number of steps taken over the baseline period / number of days with non missing data over the baseline period.
  - Baseline period is defined in section 7.1.

Daily average number of steps taken for each 7-day period is calculated as:

- Daily average number of steps taken for 7-day period = total number of steps over the period / number of days with non missing data over the period.

Change from baseline is calculated as:

- Daily average number of steps taken for 7-day period - Average baseline number of steps taken.

### **Change from baseline on Days 7, 14, and 21 in Ratio of sedentary/non-sedentary time**

Number of sedentary behaviour minutes in the day is defined as Sedentary Activity from the Day Level Activity Outcomes.

Number of non-sedentary behaviour minutes in the day is derived as:

- Sum of Light Activity and MVPA from the Day Level Activity Outcomes.

Ratio of sedentary/non-sedentary time per day is calculated as:

- Ratio of sedentary/non-sedentary time per day = Number of minutes in the day defined as Sedentary behaviour ÷ Number of minutes in the day defined as Non-Sedentary behaviour.

Baseline ratio of sedentary/non-sedentary time is calculated as described in section 7.1, where the variable of interest is the ratio of sedentary/non-sedentary time.

Ratio of sedentary/non-sedentary time for each 7-day period is calculated as:

- Ratio of sedentary/non-sedentary time for 7-day period = Total number of minutes defined as Sedentary behaviour in the 7-day period/ Total number of non-sedentary behaviour minutes in the 7-day period

Change from baseline is calculated as:

- Ratio of sedentary/non-sedentary time for 7-day period - Baseline ratio of sedentary/non-sedentary time.

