### Baseline

The baseline value for QOL data is defined as measurements collected on Day 0.

Baseline for data collected through connected activity tracker is derived as an average per day:

- Sum of the variable of interest/baseline period.

Where the baseline period is the number of non-missing days between day -6 to day 0 – Prior to product usage.

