### 8.2 Specific Methods for Efficacy Analyses

For the primary and secondary endpoints where the data is collected through the activity tracker, only subjects who meet the minimum wear threshold will be included in the analysis. This is defined as a minimum of 3 valid days during the baseline period and a minimum of 3 valid days within each post-baseline 7-day period, where a valid day is defined as a minimum wear of 20 hours per day.

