### 8.2.3 Secondary Analysis

The following secondary endpoints are analysed in the manner as described for the primary endpoint described in section 8.2.2:

- Change from baseline on Days 7, 14, and 21 in Daily Average number of steps taken.
- Change from baseline on Days 7, 14, and 21 in Ratio of sedentary/non-sedentary time.
- Change from baseline on Days 7, 14, and 21 in Gait, assessed through speed and step irregularity (measured via cadence and gait speed).
- Change from baseline on Days 7, 14, and 21 in Indices of morning stiffness (assessed through levels of mobility 30- and 60-mins post-wake).
- Change from baseline in self-reported pain intensity, assessed through Numeric Rating Scale (NRS) on Days 7, 14 and 21.
- Change from baseline in WOMAC Physical Function subscale on Days 7, 14, and 21.
- Change from baseline in the WOMAC subscales, Pain (composite) and Stiffness (composite) on Days 7, 14, and 21.
- Change from baseline in the WOMAC Global Score on Days 7, 14, and 21.

The secondary endpoint, study subjects' perceived ability to exercise more regularly, assessed using the WOMAC Physical Function subscale on Days 7, 14, and 21, will be analysed by exploring the correlation between WOMAC Physical Function subscale on Days 7, 14, and 21 and the average MVPA as detailed in section 7.4.7.1 (primary endpoint variable) graphically, by means of Spearman rank correlation.

The following secondary endpoints are analysed by descriptive statistics with no formal statistical hypothesis testing performed:

- MVPA on each day of the study (Baseline to final treatment day 21).
- Change from baseline in Karolinska Sleepiness Scale on Days 7, 14, and 21.
- Change from baseline in Health-related quality of life, EQ-5D-5L, on Days 7, 14, and 21.

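### The sedentary/non-sedentary endpoint subtracts a baseline mean of daily ratios from a post-baseline ratio of totals, so it shows a change even when behaviour has not changed

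*SAP*

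**What the plan says.** SAP 7.4.7.2 first defines a ratio for each day: "Number of minutes in the day defined as Sedentary behaviour ÷ Number of minutes in the day defined as Non-Sedentary behaviour". The denominator is "Sum of Light Activity and MVPA from the Day Level Activity Outcomes".

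For baseline it then states: "Baseline ratio of sedentary/non-sedentary time is calculated as described in section 7.1, where the variable of interest is the ratio of sedentary/non-sedentary time". The rule in SAP 7.1 is a per-day average, "Sum of the variable of interest/baseline period", where the baseline period is the count of non-missing days from Day -6 to Day 0. Baseline is therefore the unweighted mean of the daily ratios.

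For each post-baseline period the same section changes formula: "Total number of minutes defined as Sedentary behaviour in the 7-day period/ Total number of non-sedentary behaviour minutes in the 7-day period". The endpoint subtracts the first quantity from the second.

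The neighbouring tracker endpoints do not do this. For steps, the post-baseline value is "total number of steps over the period / number of days with non missing data over the period", and baseline has the same form. MVPA, cadence, gait speed and morning stiffness also use one per-day average in both periods.

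The ratio endpoint is formally tested. It is on the list in SAP 8.2.3 introduced by "The following secondary endpoints are analysed in the manner as described for the primary endpoint described in section 8.2.2". The protocol gives no formula for the ratio, and nothing in either document reconciles the two definitions.

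**The concern.** A mean of daily ratios gives every day equal weight. A ratio of totals weights each day by its non-sedentary minutes, so active days, which tend to have low ratios, count for more. Subtracting one from the other builds a difference into the endpoint that has nothing to do with treatment. It is a systematic shift in the expected change, on top of ordinary day-to-day noise.

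The usual direction is downward, towards apparent improvement. The hypothesis tested is a within-subject difference from baseline in a single-arm study, so the shift goes straight into the estimate and its p-value.

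**Working it through.** **Inputs.** From the SAP: the two formulas above, the two-sided 5% level (8.1) and 147 completers (3.2.1). The plan states no expected value or variability for this ratio, so there is no figure of its own to reproduce. All variability inputs below are assumptions.

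**Algebra.** Let S and N be daily sedentary and non-sedentary minutes and r = S/N. On the same set of days,

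ratio of totals - mean of daily ratios = cov(r, N) / mean(N),

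with the covariance taken over days (divisor equal to the number of days). It is zero only when that covariance is zero, for example when N or r is the same every day. If S + N is a constant T, then r = T/N - 1 falls as N rises, so the difference is negative whenever N varies.

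**Worked examples, identical days in both periods.**

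- 700/260 and 500/460: mean of ratios (2.692 + 1.087)/2 = 1.89; ratio of totals 1200/720 = 1.67; change -0.22.
- 800/300 and 400/200: mean of ratios (2.667 + 2.000)/2 = 2.33; ratio of totals 1200/500 = 2.40; change +0.07. The sign can reverse when total classified time varies.
- Seven days with T = 900 and N = 180, 220, 260, 300, 340, 380, 420: mean of ratios 2.244; ratio of totals 4200/2100 = 2.000; change -0.244, or -10.9%.

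**Expected shift with no true change.** Assume 960 classified minutes a day, mean N of 320, lognormal daily N with coefficient of variation CV, between-subject log SD 0.25 and seven days per period. Then E(1/N) = (1 + CV²)/mean, and for a seven-day total approximately (1 + CV²/7)/mean. The shift is about -(960/320) × exp(0.25²) × (6/7) × CV² = -2.74 × CV², which is -0.027, -0.109 and -0.246 at CV 10%, 20% and 30%. Simulation with 3 to 7 baseline days gave -0.03, -0.11 and -0.25, about -1%, -5% and -10% of baseline. The result was the same when the daily total varied by 8%. If S and N vary independently, each with CV 20%, the shift is about -(640/320) × (6/7) × 0.04 = -0.069, and simulation gave -0.069.

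**False-positive rates, n = 147, no true change, 800 replicates.**

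| Test | Week-to-week log SD | CV 10% | CV 20% | CV 30% |
|---|---|---|---|---|
| One-sample t, week 1 | 0 | 38% | 92% | 100% |
| One-sample t, week 1 | 0.15 | 7% | 32% | 87% |
| Intercept gate, then week-1 adjusted mean | 0 | 19% | 84% | 100% |
| Intercept gate, then week-1 adjusted mean | 0.15 | 12% | 43% | 91% |

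The last two rows approximate SAP 8.2.2 by ordinary least squares on complete data with uncentred baseline. With the mean of daily ratios in both periods, the t test rejected in 4% to 6% and the gated procedure in 2% to 8%.

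**A second set of assumptions.** With mean S 600 and N 300, 3 or 7 baseline days, no week-to-week variation and a Wilcoxon test of week 1, rejection was 23% to 46% at CV 10% and 61% to 95% at CV 20%. At CV 20% the spurious shift is 0.20 to 0.31 SD of the change, about the size of the 0.25 SD effect for which the study was planned.

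**The case against.** - **The size is assumed.** This stands. The documents give no day-to-day CV, classified minutes or mean ratio. The rejection rates without week-to-week variation are an extreme case. At CV 10% with week-to-week log SD 0.15, the simple t test rejects in 7%, close to nominal. The mismatch itself needs no assumption.
- **The rates are not exactly those of the plan.** This also stands. SAP 8.2.2 moves to a Friedman test if the data are non-normal, which is plausible for a skewed ratio, and does not say which conditions that test compares. If only the three weekly changes are compared, the common baseline cancels: Friedman rejects in about 5%. If baseline is a fourth condition, Friedman followed by a week-1 Wilcoxon test rejects in 19%, 81% and 99% at CV 10%, 20% and 30% with no week-to-week variation, and in 2%, 17% and 76% with log SD 0.15. On the first reading the gate would protect the test, but the reported change from baseline would still be shifted.
- **Not every subject looks improved.** Correct. With S and N independent at CV 20%, the two formulas applied to the same seven days differ negatively in 97% of subject-weeks. With separate baseline and post-baseline days, 59% of changes are negative, against 50% with one formula. The mean shift of -0.07 is the same.
- **Protocol 13.3.2 uses the last daily value up to Day 0 as baseline for secondary endpoints.** That does not help. Under stable behaviour a single daily ratio has the same expectation as the mean daily ratio. SAP 3.5 does not list this departure.
- **Either formula would do if used on both sides.** Largely true. Mean of daily ratios gives most weight to very inactive days and is undefined if N is zero. Ratio of totals is sensitive to the number of days, as set out under the fix.
- **It is one secondary endpoint among many.** True, and it limits the importance of the point.

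**Conclusion.** The concern holds. As written, SAP 7.1 and 7.4.7.2 give this endpoint a systematic shift under unchanged behaviour. The shift is zero only if the daily ratio and daily non-sedentary time are uncorrelated across days. It is certainly negative if the daily total is constant and non-sedentary time varies, and likely but not certain to be negative otherwise.

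Under the assumed CVs of 10% to 30% it is about 1% to 10% of baseline. It is of little consequence for the simple test at the low end with realistic week-to-week variation, and substantial from CV 20% upwards under the mixed-model route. No claim is made about the exact error rate of the plan. This should be corrected before the endpoint is reported as a tested result. It does not touch the primary analysis.

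**What to change.** In SAP 7.4.7.2, use one estimator and one set of days in both periods. Preferably define each post-baseline value as the sum of the daily ratios over non-missing days in the period, divided by the number of those days. This matches SAP 7.1 and the other tracker endpoints. State how a day with no non-sedentary minutes is handled.

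SAP 8.2 gives a wear rule for including subjects, "where a valid day is defined as a minimum wear of 20 hours per day". If it is also meant to select days, say so and apply it to baseline and post-baseline alike. Record in SAP 3.5 that the baseline differs from Protocol 13.3.2.

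Ratio of totals in both periods is second best because baseline can have fewer days than a post-baseline week. With 3 to 7 baseline days it left a residual shift of -0.002 to -0.03, against at most 0.005 in absolute size for the mean of daily ratios. In the second set of assumptions, with exactly 3 baseline days and CV up to 40%, the residual was -0.006 to -0.09 and rejection 4.5% to 13%. With 7 baseline days it was negligible.

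The cost is one line of SAP text and one ADaM derivation, which SAP 5.3 requires to be double-programmed, and no new data. As SAP 2.0 already carries changes from the data review meeting, the reason for this one should be documented as a correction of the formula that does not depend on results.

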### **Change from baseline on Days 7, 14, and 21 in Gait, assessed through speed and step irregularity (measured via cadence and gait speed)**

Average baseline cadence is calculated as:

- Average baseline cadence = total mean cadence over the baseline period / number of days with non-missing data over the baseline period.
  - Baseline period is defined in section 7.1.

Average cadence for each 7-day period is calculated as:

- Average cadence for 7-day period = total mean cadence / number of days with non missing data over the period.

Change from baseline is calculated as:

- Average cadence for 7-day period - Average baseline cadence.

Average baseline gait speed is calculated as:

- Average baseline gait speed = total mean gait speed over the baseline period / number of days with non-missing data over the baseline period.
  - Baseline period is defined in section 7.1.

Average gait speed for each 7-day period is calculated as:

- Average gait speed for 7-day period = total mean gait speed / number of days with non missing data over the period.

Change from baseline is calculated as:

- Average gait speed for 7-day period - Average baseline gait speed.

**Change from baseline on Days 7, 14, and 21 in Indices of morning stiffness (assessed through levels of mobility 30- and 60-mins post-wake)**

30 minutes post-wake is defined as the interval from bed interval end date/time from the Sleep Metrics by Night Outcome + 30 minutes.

Daily morning stiffness 30 minutes post-wake is defined as the total vector magnitude counts 30 minutes post-wake.

Average baseline morning stiffness 30 minutes post-wake is calculated as:

- Average baseline morning stiffness 30 minutes post-wake = total Daily morning stiffness 30 minutes post-wake over the baseline period / number of days with non-missing data over the baseline period.
  - Baseline period is defined in section 7.1.

Average morning stiffness 30 minutes post-wake for each 7-day period is calculated as:

- Average morning stiffness 30 minutes post-wake for 7-day period = total Daily morning stiffness 30 minutes post-wake / number of days with non missing data.

Change from baseline is calculated as:

- Average morning stiffness 30 minutes post-wake for 7-day period - Average baseline morning stiffness 30 minutes post-wake.

60 minutes post-wake is defined as the interval from bed interval end date/time from the Sleep Metrics by Night Outcome + 60 minutes. Daily morning stiffness 60 minutes post-wake, average baseline morning stiffness 60 minutes post-wake, average morning stiffness 60 minutes post-wake for each 7-day period and change from baseline are calculated in the same way as described for 30 minutes post-wake.

